This is a two group, parallel randomized non-inferiority clinical trial at one institution evaluating telephone postoperative visits as non-inferior in patient satisfaction, patient preference, and patient safety, when compared with clinic postoperative visits. This protocol was written in accordance with CONSORT (Consolidated Standards of Reporting Trials) guidelines 2011.

VI: Methods:

A. Study Setting:

Patient recruitment will come from women presenting for their follow up clinic visit at the University of South Florida's (USF) Female Pelvic Medicine and Reconstructive Surgery (FPMRS) Clinic. Women who present to this follow up clinic visit have already been seen and evaluated within USF's FPMRS clinic by one of the FPMRS faculty, have undergone appropriate testing and are now receiving detailed, focused counseling in order to decide upon preferred surgical management. At this point a letter is sent to schedule the desired procedure. Once the physician and patient have agreed upon the surgical management plan it is the routine practice, at our institution, to submit a letter to the surgical scheduler. The letter details the type of surgery, medical clearance requests, and postoperative follow up. The patient is informed that she will be contacted, by our office, in the next two weeks and provided with all necessary information and documentation, including date of surgery and follow up appointments. It will be at this follow up clinic visit that patients will be told about our study and consented if applicable.

B. Eligibility:

The women that present to the USF FPMRS follow up visit and have decided to undergo surgical management of prolapse or incontinence, will be assessed to determine if they meet eligibility requirements. Eligibility requirements are as follows:

1. Inclusion Criteria:

- Women >18 desiring surgical management of prolapse or incontinence
- English speaking
- Willing and able to provide written and informed consent without assistance from medical surrogate or interpreter

- Immediate access to telephone services (landline, mobile phone, office phone)

2. Exclusion Criteria:

- Women <18
- Non-English speaking
- Unwilling and unable to provide written and informed consent without assistance from surrogate or interpreter
- Hearing impairment
- No access to telephone services (landline, mobile phone, office phone)
- Grade 3 complication- a complication requiring surgical, endoscopic, or radiological intervention. [3]

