Vital signs and physical examination will be deferred for the patients in the telephone follow up group. The clinic visit will entail questions about common postoperative complications (including fever, nausea/vomiting, pain, urinary symptoms, constipation, etc.). As per usual, vital signs and a focused physical examination will be completed at the clinic visit. All clinic visits will be performed by an FPRMS fellow and/or attending physician. At the end of each visit (telephone and clinic) patient will be reminded about postoperative restrictions as outlined in discharge instructions. The length of duration of both the telephone and clinic visits will be recorded by documenting the start and end time. For the clinic visit the start time will be the time patient is documented as “arrived” status in waiting area and finish time when the physician leaves the room. For the telephone visit, the start time will be at the time the patient answers the phone and finish time when phone call ends. Both clinic and telehealth visits will be documented with progress notes in EMR.

D. Randomization

Eligible patients will be randomized to Arm1 or Arm2 (Telephone follow up or clinic follow up). Permuted block randomization with randomly varying block sizes will be used. Generation of allocation sequences will be performed using a random-number table.

E. Concealment of Treatment Allocation:

The allocation sequence will be generated by our statistician who is neither responsible for patient recruitment or outcome assessment. Sequentially numbered opaque sealed envelopes will be used for concealment of treatment allocation.

F. Blinding:

It is not possible to mask clinical staff or participants, as they will be aware of the follow-up care that is being delivered over the telephone or in clinic. As such this is not a blinded study. The surgical scheduler will open the sealed randomization envelope revealing the patient’s allocated intervention and document this in the patients’ chart. The PI will keep the master link matching the patient to the allocated intervention. The PI is also responsible for entering all collected data into a de-identified excel spreadsheet.

VII. Outcomes

A. Primary:

- Comparison of patient satisfaction as determined by completion of a non-validated, treatment non-specific satisfaction questionnaire between the two groups. Survey will be provided at the six-week follow up visit.

B. Secondary:

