- Comparison of adverse events and Emergency Department (ED) visits between the two groups. Will be determined by reviewing the patient's record to identify adverse events as defined below. Informed consent will include consent to obtain outside ED records; as this is standard practice for patients seen in ED during perioperative/postoperative period.
- Actual time spent on phone call during postoperative telephone follow up compared to time spent in clinic follow up measured in minutes.
- Correlation, between groups, of overall patient's satisfaction with subjective measures, complications, demographics, and travel distance.

VIII. Data Collection:

At the initial visit, once eligibility status is determined and consent is obtained, data collection form will include demographics, distance traveled, complications, and number of ED visits, type of surgery performed etc. Also patients will complete three postoperative patient satisfaction questionnaires at the six-week postoperative clinic visit. This will include the Patient Satisfaction Questionnaire (PSQ) 18 Short Form, a validated questionnaire. Also will include the Patient Global Impression of Improvement (PGII), a validated questionnaire. And a three-question survey about patient satisfaction with the postoperative experience, not validated. All six -week visits will be in person. The questionnaires will be completed before the physician interviews the patient. These questionnaires will be stored in a locked filing cabinet and later transferred by the PI to an excel spreadsheet stored on a password-protected computer. Additionally, pertinent medical information will be extracted from the patient's medical chart, de-identified, and transferred to the an excel spreadsheet after surgery by a member of the study team, including socio-demographic data, perioperative and postoperative details, adverse events, and ED visits.

Adverse events are defined based on previous studies [4, 5,]

- bladder injury
- ureteral injury
- bowel injury

- operative estimated blood loss >500mL
- reoperation < 30 days
- hematoma
- pelvic abscess
- vaginal cuff cellulitis
- ileus
- small bowel injury
- transfusion
- pulmonary
- cardiac
- neurological injury
- urinary tract infection (culture proven, urinalysis with presence of leukocyte esterase, nitrites, or blood, symptoms of infection)
- pyelonephritis
- urinary retention (more than 6 week postoperative)
- mesh erosion
- incisional hernia
- wound complication

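### The urinary tract infection definition lets blood alone make a urinalysis positive and does not say how culture, urinalysis and symptoms combine, so the event count depends on how an unblinded abstractor reads it.

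*Combined protocol and SAP*

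**What the plan says.** Section VII.B makes safety a secondary outcome: "Comparison of adverse events and Emergency Department (ED) visits between the two groups". Events are found by chart review: "Will be determined by reviewing the patient's record to identify adverse events as defined below". The list follows in section VIII (Data Collection) and has about 20 items. It is attributed to two cited studies, and the plan does not reproduce their definitions.

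The item at issue reads "urinary tract infection (culture proven, urinalysis with presence of leukocyte esterase, nitrites, or blood, symptoms of infection". Commas separate three elements: culture, urinalysis and symptoms. The only 'or' lies inside the urinalysis element, where it puts blood on the same footing as leukocyte esterase and nitrites. No 'and' or 'or' joins the three elements.

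Other relevant text:
- Eligibility (VI.B) is "Women >18 desiring surgical management of prolapse or incontinence", so every participant is planned for pelvic surgery.
- At two weeks, "Vital signs and physical examination will be deferred for the patients in the telephone follow up group"; for the other arm, "As per usual, vital signs and a focused physical examination will be completed at the clinic visit" (VI.C). Neither sentence mentions a urinalysis.
- On masking: "As such this is not a blinded study" (VI.F). The scheduler documents the allocation in the patient's chart, and section VIII has a member of the study team extract adverse events from that chart.
- Section X (Proposed Analyses) gives chi-square or t-tests at p<0.05 and states no margin for safety.

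**The concern.** An abstractor needs a rule that gives the same answer for the same record, and this one does not. A chart showing only blood on a urinalysis is an event under one reading and not under the other. So is a chart with symptoms and no urine result. Whoever decides can see the arm.

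At stake is the safety comparison. The hypothesis in section III calls telephone follow-up safe, and section V lists patient safety among the things to be shown non-inferior. Misclassified events pull a real difference between arms towards zero. Section VII.B also relates complications to satisfaction, so the same error would enter a second analysis.

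**Working it through.** **1. Check of the plan's own figure.** Inputs from section IX (Sample Size): proportions 0.87 and 0.90, margin 0.12, one-sided 0.025, 80% power, unpooled variance. The variance sum is 0.87×0.13 + 0.90×0.10 = 0.2031. Then n = (1.960 + 0.842)² × 0.2031 / (0.12 + 0.03)² ≈ 70.8, so 71 per group, with power 80.1%. The stated figure reproduces. It concerns satisfaction, so the infection definition has no bearing on it.

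**2. The two readings applied to the same record.**

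| Record | Any one element suffices | All three required |
|---|---|---|
| Blood only on urinalysis; no culture, no symptoms | counted | not counted |
| Symptoms only | counted | not counted |
| Symptoms and nitrites, no culture | counted | not counted |
| Positive culture, positive urinalysis, symptoms | counted | counted |

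The first two rows may be over-counting under one reading. The third is under-counting under the other.

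**3. Effect of over-counting, illustrated.** The documents give no infection rate and no false-positive rate, so everything here except n = 71 is assumed. Let p be the true rate and f the share of uninfected women coded as infected, equal in both arms. Then:
- observed rate = p + (1 − p)f
- observed difference = (1 − f) × true difference
- SE = √[p₁(1 − p₁)/71 + p₂(1 − p₂)/71], using observed rates.

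With true rates of 5% (clinic) and 15% (telephone):

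| f | Observed rates | Difference (points) | Risk ratio | z | Upper 95% limit (points) |
|---|---|---|---|---|---|
| 0 | 5.0% vs 15.0% | 10.0 | 3.00 | 2.01 | 19.7 |
| 5% | 9.75% vs 19.25% | 9.5 | 1.97 | 1.62 | 21.0 |
| 10% | 14.5% vs 23.5% | 9.0 | 1.62 | 1.38 | 21.8 |
| 20% | 24.0% vs 32.0% | 8.0 | 1.33 | 1.07 | 22.7 |

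With assumed true rates of 10% and 20%, power for a two-sided 5% test is 38% at f = 0, 30% at 5%, 24% at 10% and 17% at 20%. The risk ratio goes from 2.00 to 1.66, 1.47 and 1.29.

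**4. Effect of under-counting.** If only a share s of true infections meets all three requirements, equal in both arms, the observed rates are s × p. The difference becomes s × the true difference, again nearer zero, and the risk ratio is unchanged.

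**5. If urine testing differs by arm.** The documents do not say who is tested. Suppose all clinic patients and half of telephone patients are tested, false positives arise only in those tested, and the true rate is 10% in both arms. At f = 10% the observed rates are 10% + 90% × 10% = 19.0% and 10% + 90% × 10% × 0.5 = 14.5%. At f = 20% they are 28.0% and 19.0%. Telephone would look safer by 4.5 or 9.0 points with no true difference.

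**The case against.** Four objections carry weight.

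*The text does not establish that non-infections will be counted.* A reader might infer that blood alone is enough for an event. It is enough for a positive urinalysis, but if all three elements are required it never makes an event. This stands: the certain defect is the undefined rule, and over-counting depends on the reading used.

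*No urinalysis schedule is given.* A reader might picture samples taken soon after surgery, when blood without infection would be likely. The plan does not say when or in whom urine is tested, and how often blood appears without infection is not in the documents. Nor does it equate symptoms of infection with the urinary symptoms asked about at follow-up. These points stand, so f is unknown.

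*The error need not favour telephone follow-up.* This is the most tempting stronger reading. It holds only if a non-significant chi-square result is taken as evidence of safety, and the plan states no such rule. Judged by a confidence interval, over-counting works the other way: the upper limit for harm rises from 19.7 to 21.8 points at f = 10%. With equal true rates of 10%, the half-width grows from 9.9 to 12.9 points. The missing safety margin is a separate weakness that a better definition would not cure.

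*The 5% versus 15% illustration is flattering.* It starts at z = 2.01, so any dilution appears to lose significance. Power there is only about 51% with perfect coding. The nearest whole counts, 4 and 11 of 71, give a Pearson z of 1.91, already non-significant. The risk ratio also falls much more sharply than the difference. The table shows mechanism and direction, and does not estimate the effect.

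The independent urologist's three reviews (Data and Safety Monitoring) partly answer the concern about oversight, but they are not described as event coding or as masked.

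**Conclusion.** The definition is ambiguous on its face and makes blood sufficient for a positive urinalysis. Different abstractors could reach different counts from the same charts, and allocation is visible when the reading is chosen.

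The consequence is misclassification in one item of about 20 within a secondary outcome. If the error is equal in both arms, it moves the difference towards zero under either reading. Over-counting also widens the confidence interval in the illustrations. In those, the difference loses 0.5 to 2.0 points out of 10 as f goes from 5% to 20%. The documents do not allow the actual size to be worked out, nor do they show unequal testing between arms. The primary outcome and the 71 per group are unaffected.

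This is a modest point, worth settling before coding because a rule chosen afterwards in an unblinded trial would be hard to defend.

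**What to change.** For outcome counting only, with no change to testing or care:

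1. Remove blood as a sufficient urinalysis finding and state how the elements combine before coding starts. One workable rule is: culture-proven, or symptoms of infection plus a urinalysis positive for nitrites or leukocyte esterase. This keeps culture-proven cases that have no recorded symptoms.
2. Abstract culture, each urinalysis marker and symptoms as separate fields, and apply the rule to those fields with the arm column removed. Study IDs alone do not mask coding, because the allocation is written in the chart being abstracted.
3. Report by arm the number of symptomatic women with no urine test. They leave the count under this rule, and the table shows whether they leave it unequally.
4. Report culture-proven infection as a sensitivity count.

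The cost is one revised definition, a few more abstraction fields and a masked coding step. Fewer infections may be counted.

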- reoperation for complication of surgery
-

IX. Sample Size:

Sample sizes of 71 in Group 1 and 71 in Group 2 achieve 80% power to detect a non-inferiority margin difference between the group proportions of -0.12. The traditional office visit group proportion is 0.87. The Telehealth group proportion is assumed to be 0.75 under the null hypothesis of inferiority. The power was computed for the case when the actual Telehealth group proportion is 0.90. The test statistic used is the one-sided Z test (unpooled). The significance level of the test is 0.025.

X: Proposed Analyses:

Data analyses will be performed at the University of South Florida in Tampa, Fl. Data management and analyses will be conducted using SAS version 9.4 (SAS Institute, Inc, Cary, North Carolina). Subject demographic characteristics such as age, distance traveled, surgical procedures, ED visits will be summarized by standard descriptive statistics (e.g. means and standard deviations or median (range) for continuous variables and percentages for categorical variables. The difference between groups will be compared using the chi-square test or t-test, as appropriate. Logistic linear regression will be used to evaluate independent predictors for patient satisfaction. A p-value <0.05 will be considered statistically significant.

VIII. Confidentiality

At all times, appropriate measures will be taken to protect the confidentiality of all study participants in accordance with HIPAA guidelines. Patients will be approached for recruitment in private patient exam rooms. Once enrolled, all patients will be administered a study ID number starting with 1 and proceeding numerically. A master link between the individual subjects and their study ID number will be stored in a secure location (on a password-protected computer in the Urogynecology Fellows' office). All data collection forms (DCF) and stored patient information will only contain the study ID number. Charts will be reviewed in a secure location at all times. Upon completion of the data collection period, all information will be entered into an excel spreadsheet on a password-protected computer for data analysis.

IX Safety

This a voluntary study. Patients have the right to refuse to participate.

Data and Safety Monitoring

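### The unpooled Z test named in Section IX has an exact one-sided error of 2.8%, not 2.5%, at the plan's own null; Section X should name a score test instead

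*Combined protocol and SAP*

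**What the plan says.** Section IX (Sample Size) gives a full set of inputs. The size and power are "Sample sizes of 71 in Group 1 and 71 in Group 2 achieve 80% power", for a "non-inferiority margin difference between the group proportions of -0.12". On the clinic arm: "The traditional office visit group proportion is 0.87". On the null: "The Telehealth group proportion is assumed to be 0.75 under the null hypothesis of inferiority". On the alternative: "The power was computed for the case when the actual Telehealth group proportion is 0.90". On the test: "The test statistic used is the one-sided Z test (unpooled). The significance level of the test is 0.025".

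The section mentions no score test, exact test or continuity correction, and no check of the level actually achieved.

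Section X (Proposed Analyses) names no non-inferiority test. Groups are to be compared by chi-square or t-test, predictors of satisfaction by logistic regression, and significance is set at p<0.05. The margin does not appear there.

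**The concern.** The unpooled (Wald) Z statistic takes its standard error from the observed proportions. When both proportions are high, that standard error tends to be too small in the very samples where telephone happens to look good. The statistic then crosses 1.96 more often than 2.5% of the time when telephone is truly 12 points worse.

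The direction matters in a non-inferiority trial, because the error favours the conclusion the trial hopes to reach. Section X offers no other margin-based test, so an analyst looking for one would find only the unpooled Z. A borderline result could then depend on a variance estimator that nobody chose deliberately for the analysis.

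**Working it through.** **Inputs, all from Section IX:** n = 71 per arm; margin -0.12 (telephone minus clinic); clinic 0.87; telephone 0.75 under the null and 0.90 under the alternative; one-sided level 0.025, so the critical value is 1.96.

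**1. Reproduce the plan's figure.** For the unpooled Z,

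n = (z_α + z_β)² × [p_C(1−p_C) + p_T(1−p_T)] / (p_T − p_C + margin width)²

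With z_α = 1.960 and z_β = 0.842, the squared sum is 7.85. The variance term, 0.87×0.13 plus 0.90×0.10, is 0.2031. The distance from the margin, 0.90 minus 0.87 plus 0.12, is 0.15, and its square is 0.0225. So n = 7.85 × 0.2031 ÷ 0.0225 = 70.9, which rounds up to 71.

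The standard error at 71 is √(0.2031 ÷ 71) = 0.0535. Then 0.15 divided by 0.0535, less 1.96, is 0.845, and approximate power is 0.801. The plan's 71 and 80% reproduce.

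**2. Exact type I error.** Let X (telephone) and Y (clinic) be independent binomial counts out of 71, with the telephone rate equal to the clinic rate minus 0.12. For each of the 72 × 72 possible tables, declare non-inferiority when

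(p̂_T − p̂_C + 0.12) / √[p̂_T(1−p̂_T)/71 + p̂_C(1−p̂_C)/71] ≥ 1.96,

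and add up the probabilities of the tables that qualify. For the Farrington-Manning score test, replace the two proportions in the variance by their maximum-likelihood estimates constrained to differ by exactly 0.12.

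| Clinic rate | Telephone rate | Unpooled Z | Score test |
|---|---|---|---|
| 0.80 (assumed) | 0.68 | 0.0267 | 0.0257 |
| **0.87 (plan)** | **0.75** | **0.0282** | **0.0246** |
| 0.90 (assumed) | 0.78 | 0.0293 | 0.0246 |
| 0.95 (assumed) | 0.83 | 0.0358 | 0.0228 |
| 0.98 (assumed) | 0.86 | 0.0409 | 0.0204 |

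At the plan's null the excess is 0.0282 minus 0.025, or 0.0032, about 3 extra false declarations per 1,000 null trials. At 0.95 the ratio is 0.0358 ÷ 0.025 = 1.43. The unpooled Z error rises without interruption as the clinic rate goes from 0.80 to 1.00. A simulation of 2 million trials per point agrees: 0.0283 at clinic rate 0.87; 0.0293 at 0.90; and 0.0360 at 0.95.

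**3. Is it peculiar to 71?** No. At sizes from 60 to 90 per arm in steps of 3, the unpooled Z error is 0.027 to 0.029 at clinic rate 0.87; 0.028 to 0.030 at 0.90; and 0.032 to 0.037 at 0.95.

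**4. Exact power at 0.90 against 0.87, 71 per arm.** Unpooled Z 0.807; score test 0.774. The gap of 3.3 points is the share of trials called non-inferior by the first test and not by the second; essentially none go the other way.

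**5. A table where they differ.** Telephone 63 of 71, a proportion of 0.8873; clinic 64 of 71, a proportion of 0.9014. The difference plus 0.12 is 0.1059.
- Unpooled: the variance sum, 0.8873×0.1127 plus 0.9014×0.0986, is 0.1889. The standard error is √(0.1889 ÷ 71) = 0.0516 and z = 2.05, non-inferior.
- Score: the constrained estimates are 0.8124 and 0.9324. The variance sum, 0.8124×0.1876 plus 0.9324×0.0676, is 0.2154. The standard error is √(0.2154 ÷ 71) = 0.0551 and z = 1.92, not non-inferior.

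**6. Other simple remedies.** Pooling the variance leaves the error unchanged at these rates (0.0282 at 0.87). A continuity correction lowers it to 0.016 at 0.87 but cuts exact power to 0.73.

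**The case against.** The strongest objection is that the unpooled Z is named only to describe the power calculation. A reader might infer that the trial, as planned, will be too ready to call telephone non-inferior. The documents do not support that: Section X never commits to the unpooled Z, or to any margin-based test. This stands, so the point is conditional on that test being used, and the change has to reach Section X as well as Section IX.

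Second, the effect is small where the plan expects to be. For clinic counts from 58 to 69 out of 71, the two tests need the same telephone count in 7 of 12 cases and differ by one patient in the other 5. This also stands. A reader might take 3.6% or 4.1% as the trial's error rate, but those figures need clinic rates of 0.95 or 0.98, which the documents do not give.

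Third, the score test is also a large-sample method: 2.6% at a clinic rate of 0.80 and 2.0% at 0.98. True, but it stays closer to 2.5% than the unpooled Z throughout the table, and any excess is about 0.1 point.

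Fourth, the plan does not say which questionnaire response counts as satisfied, and that comes before any choice of variance. This is fair, but it does not remove the need to name a test.

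Finally, a reader might infer that the sample size is miscalculated. It is not, as step 1 shows.

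**Conclusion.** The point holds as a minor one. If the unpooled Z decides the primary outcome at 71 per arm, the one-sided error at the plan's own null is 2.8% rather than the stated 2.5%, in the anti-conservative direction. It would be material only if clinic satisfaction were about 0.95 or higher, which is an assumption and not a figure in the plan.

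The result rests on independent binomial outcomes, a yes/no satisfaction endpoint and 71 analysed per arm. Smaller or larger arms between 60 and 90 give the same picture.

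**What to change.** - **Section X:** name the Farrington-Manning score test against -0.12 at one-sided 0.025 as the primary analysis, and report the Miettinen-Nurminen 95% confidence interval with it. In the SAS version already planned, the test is PROC FREQ with RISKDIFF(NONINF MARGIN=0.12 METHOD=FM). The interval carries an extra variance factor of 142/141, so state that the test decides if the two ever differ in a borderline table.
- **Section IX:** replace the unpooled Z with the same test and restate the power as about 77% at 71 per group.

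The cost is one analysis option and about 3 points of stated power at the same size. If the sponsor wants to keep 80%, about 76 per arm gives exact power of 0.806 with the score test, which is 2 × 5 = 10 more patients. The choice should be fixed before any outcome data are seen.

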In the setting of urogynecological procedures, the use of telephone follow up is an area that needs to be studied. There is no known standardization about how postoperative follow up visits are conducted after pelvic reconstructive surgery. There is much variation amongst providers concerning when and how postoperative follow up visits are completed. With the advances in robotic and laparoscopic procedures, hospital length of stay has decreased significantly. We now must examine the benefits of minimally invasive surgery as it relates to postoperative follow up. If in person postoperative visits can be replaced with telephone visits, we can possibly increase patient satisfaction. By allowing the patient to have a postoperative visit in the comfort of her own home, we can save her travel costs and travel time. Additionally, in our practice, the in person postoperative visits can ultimately be replaced with procedures and established patient visits, ultimately allowing for more availability for new patient consultations. By evaluating the use of telephone follow up, versus clinic follow up we will show that patient satisfaction with telephone follow up will be unchanged or improved compared to our standard practices.

II. Objective:

A. Primary Aim(s):

- To determine if patient satisfaction with postoperative care with telephone follow up is non-inferior to clinic follow up.

B. Secondary Aim(s):

- To determine if telephone postoperative follow up is a safe alternative to clinic postoperative follow up visits
- To determine if telephone or clinic follow up visits are preferred based on differing demographics (i.e. age, race, distance traveled, outpatient versus inpatient surgery).
- To determine length of visit differences between telephone and clinic follow up.

III. Hypothesis:

For the standard two-week postoperative visit, follow up telephone calls will be non-inferior to traditional office visits. The telephone visit is a safe and efficient alternative to the in person visit following urogynecological procedures.

a. H_0 Traditional office visits are superior to follow up via telephone calls for two-week postoperative visits.

IV. Interventions:

Scheduled telephone call at the two-week postoperative visit completed by the urogynecology clinic nurse.

V. Study Design:

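### Section X does not carry the non-inferiority test of Section IX into the primary analysis; its only between-group comparison is a chi-square or t-test for a difference

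*Combined protocol and SAP*

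**What the plan says.** Section II.A sets the primary aim: "To determine if patient satisfaction with postoperative care with telephone follow up is non-inferior to clinic follow up". Section III words the null hypothesis as "Traditional office visits are superior to follow up via telephone calls for two-week postoperative visits", with no margin.

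Section IX (Sample Size) gives a full set of design inputs. The margin is -0.12 on the difference in proportions, the clinic proportion is 0.87, and the telephone proportion is 0.75 under the null and 0.90 for the power calculation. It adds "The test statistic used is the one-sided Z test (unpooled). The significance level of the test is 0.025". These are stated as the basis for "Sample sizes of 71 in Group 1 and 71 in Group 2 achieve 80% power".

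Section X (Proposed Analyses) first lists descriptive summaries of patient characteristics. Three inferential sentences follow:

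- On comparing the arms, without naming an outcome: "The difference between groups will be compared using the chi-square test or t-test, as appropriate"
- On satisfaction, without naming study arm or margin: "Logistic linear regression will be used to evaluate independent predictors for patient satisfaction"
- On the threshold, without saying whether it is one-sided or two-sided: "A p-value <0.05 will be considered statistically significant"

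Section VII.A describes the primary outcome only as a comparison of satisfaction between the groups. Section VIII (Data Collection) identifies the non-validated instrument as "a three-question survey about patient satisfaction with the postoperative experience, not validated".

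**The concern.** A non-inferiority claim needs a test against the margin, or equivalently a confidence limit compared with it. Section X has neither, and there are two ways to read its chi-square or t-test sentence.

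- **It covers satisfaction.** It then tests whether the groups are equal, which is not the primary question.
- **It covers only the characteristics listed just before it.** Section X then contains no between-arm analysis of the primary outcome. The one sentence that names satisfaction is a regression for predictors, and it mentions neither study arm nor margin.

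On either reading, an analyst who follows Section X would not produce the result the trial was sized to give. A difference test could support non-inferiority only by coming out significantly in favour of telephone, which is unlikely under the design assumptions. The silence also leaves room for a non-significant difference to be reported as non-inferiority. The study is unblinded, so the decision rule should be fixed in writing before anyone sees the data.

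**Working it through.** **Inputs (all from Section IX).** Clinic proportion 0.87; telephone proportion 0.90 (design case) or 0.75 (null); margin 0.12; one-sided alpha 0.025; power 80%; 71 per group.

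**1. Reproduce the sample size.**

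n = (z₀.₉₇₅ + z₀.₈₀)² × [p_C(1 − p_C) + p_T(1 − p_T)] / (p_T − p_C + 0.12)²

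= (1.960 + 0.842)² × (0.87 × 0.13 + 0.90 × 0.10) / (0.03 + 0.12)² = 70.85, so 71 per group.

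Power at 71 per group is 80.1% by normal approximation and 80.7% exactly. The plan's figure is therefore correct for the Section IX test.

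**2. Compare the two tests over all possible trials.** I enumerated all 72 × 72 pairs of counts with binomial weights, clinic at 0.87. For each pair:

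- Section IX test: passes if d − 1.96 × √[p̂_C(1 − p̂_C)/71 + p̂_T(1 − p̂_T)/71] > −0.12, where d = p̂_T − p̂_C.
- Chi-square: uncorrected, two-sided 0.05.

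| Result | Telephone 0.90 (design case) | Telephone 0.75 (at the margin) |
|---|---|---|
| Section IX test passes | 80.7% | 2.8% |
| Chi-square non-significant | 91.5% | 54.7% |
| Non-significant, Section IX passes | 72.7% | 2.8% |
| Non-significant, Section IX fails | 18.7% | 51.9% |

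In the design case chi-square significantly favours telephone in 7.9% of trials and clinic in 0.6%. For 80% power to detect 0.87 versus 0.90, a difference test would need 1774 per group. The 2.8% is the exact error rate of the unpooled Z test at this sample size; its nominal level is 2.5%.

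**3. Single-trial examples, clinic 62/71.**

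| Telephone | Difference | 95% CI (unpooled) | Chi-square p | Section IX test |
|---|---|---|---|---|
| 53/71 | −0.127 | −0.254 to +0.001 | 0.054 | fails |
| 57/71 | −0.070 | −0.191 to +0.050 | 0.25 | fails |
| 61/71 | −0.014 | −0.126 to +0.098 | 0.81 | fails |
| 62/71 | 0.000 | −0.109 to +0.109 | 1.00 | passes |

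Chi-square is non-significant for telephone counts 53 to 68, while the Section IX test needs at least 62. For counts 53 to 61 the difference is non-significant but non-inferiority is not shown. At 53/71 the point estimate itself is already past the margin.

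**The case against.** The strongest reply is that the test is already in the plan. Section IX stands directly above Section X and gives margin, null value, statistic and alpha, so a reader of this short document can work out the intended primary test. That is fair: the fault is a missing link between two sections, not the absence of any test. But Section IX presents these items as inputs to a power calculation, Section X names other tests without referring to it, and no section states a criterion for declaring non-inferiority.

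The chi-square sentence may well concern only patient characteristics. That also stands as a reading, but it leaves Section X with no primary comparison at all.

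The 54.7% and 51.9% figures depend on a rule the protocol never states, and on a true telephone rate exactly at the margin. They illustrate a possible misreading and are not an error rate of this plan. The design-case figures do not need that rule.

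Finally, p<0.05 need not conflict with alpha 0.025, since a two-sided 95% interval compared with the margin gives a one-sided 0.025 test. This is correct if that is what is meant, but Section X does not state it. Applied to the one-sided non-inferiority test, 0.05 would give an exact type I error of 5.5% at the margin.

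**Conclusion.** The concern holds and must be fixed before analysis. The sample size is right for the Section IX test, but Section X as written does not answer the primary question on either reading of its chi-square sentence. The core conclusion rests on the text alone. Its size, a success rate of 80.7% for the planned test against 7.9% for a significant chi-square favouring telephone, rests on the Section IX proportions, 71 evaluable patients per group, a binary satisfaction outcome and an uncorrected chi-square. The missing margin in the Section III null hypothesis is a lesser part of the same gap.

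**What to change.** 1. In Section X, state the primary analysis. H0: p_telephone − p_clinic ≤ −0.12. Estimate the difference in the proportion satisfied with a two-sided 95% confidence interval, using the unpooled variance as in Section IX. Declare non-inferiority only if the lower limit is above −0.12, which is the one-sided 0.025 test.
2. State that the chi-square test, the t-test and the 0.05 threshold apply to baseline and secondary comparisons only.
3. Restate the null hypothesis in Section III with the margin.
4. Before analysis, name the item of the three-question survey, and the responses to it, that count as satisfied. The test needs a proportion and cannot be run without this. It is a substantive choice for the investigators.

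The cost is protocol and SAP wording plus the decision in step 4. The sample size stays at 71 per group, with no extra patients or data.
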